7. OUTCOME ASSESSMENTS

7.1. Primary Endpoint

The primary endpoint is the composite of major or clinically relevant non-major bleeding (MCRB) defined according to the ISTH-defined bleeding definitions, analyzed as time to first occurrence of any component.

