11.2. General Statistical Considerations

All analyses will be performed on observed data only. No missing data will be imputed. Data on subjects who do not reach a specific endpoint will be censored in the corresponding statistical analyses.

Raw data will be presented with the exact precision (decimal points) with which it was collected.

The p-values will be presented in the end-of-text tables exactly as they are in supporting statistical documents (4 decimal points). The text and in-text tables will display p-values with three decimal places, as long as, the decision for statistical significance will not be changed by rounding.

The number of decimal places to display for calculated data will be determined by the scale of measurement. No decimal places will be displayed if the smallest calculated value is ≥ 100 ; One (1) decimal place will be displayed when all calculated values are within the interval (10, 100), with 10 being inclusive; Two (2) decimal places will be displayed when all calculated values are within (1, 10), with 1 being inclusive; and so on for even smaller scales of measurement. Percentages will be reported with exactly one decimal place.

For continuous variables, statistical summaries will include n (number of subjects with non-missing data), mean, median, standard deviation, minimum and maximum: Means and medians will be displayed to one more decimal places than the raw or calculated data; standard deviation and other dispersion statistics will have two more decimal places; and minimum and maximum values will be displayed to the same number of decimal places as the raw or calculated data.

For categorical variables, statistical summaries will include counts and percentages. Percentages will be reported with exactly one decimal place. In general, percentages are based on the total number of subjects with information available (ie non-missing data). For AE and incidence based analyses, percentages will be based on the total number of subjects in the analysis set of interest and in that treatment regimen.

The statistical data analysis will be performed by a CRO under the guidance of the study biostatistician using SAS Version 9.3 or higher.

Definition of terms:

'Overall Study Period': This period is defined as the time from the reference date (date and time of randomization or date and time of first study edoxaban or study VKA intake) to Day 365.

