'Overall Study Period = 30 days': This period is defined as the time from the reference data (date and time of randomization or date and time of first study edoxaban or study VKA intake) to Day 395.

'Initial dose to Final Dose + 30 days': This period is defined as the time-period between the date and time of initial dose of study edoxaban or study VKA and the date and time of final dose of study edoxaban or study VKA plus 30 days, including study regimen interruptions.

Follow-up is censored at the last date of known follow-up status in subjects with incomplete follow-up. Investigators are instructed to complete follow-up as much as possible irrespective of changes or discontinuation of study medication.

When using the ITT analysis set, the reference date is the date and time of randomization, whereas in mITT and PP analyses, the reference date is the date and time of first intake of study edoxaban or study VKA.

The main analyses of adjudicated primary and secondary exploratory endpoints (Section 7.1 and 7.2, respectively) will be based on ITT analysis set and takes the first adjudicated event during the 'overall study period' into account.

However, in supplemental analyses, other combinations of analysis sets and analysis periods may be considered to evaluate the robustness of the main analyses on adjudicated safety or efficacy endpoints. Details on these analyses will be described in the SAP.

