11.4. Statistical Analysis

For each of the primary and secondary exploratory endpoints, appropriate summary statistics (e.g. event rate) including 95% CI will be provided.

For each of the endpoints, the time from reference date to the first occurrence of an event (based on CEC adjudication), is analyzed using a Cox proportional hazard model with treatment regimen as a factor and all the stratification factors from the randomization (IXRS) as covariates, to provide point estimates and 95% Confidence Interval (CI) for the hazard ratio (HR). Depending on the analysis period used in the statistical analysis, subjects without an occurrence of an event will be censored at the last date of the analysis period or at the last date of known outcomes status. The latter is determined on an individual basis for subjects with incomplete follow-up.

The parameter estimate β (= \ln (Hazard ratio)), its standard error, p-value, and 95% Confidence Limits are calculated according to the maximum partial likelihood method (ML), with Breslow's approximation for ties (SAS PHREG procedure).

For time to first event analyses based on the 'overall study period', cumulative event rates over time are summarized using the Kaplan-Meier method.

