17.3. ISTH Bleeding Criteria

Table 17.1 : ISTH Bleeding Criteria

ISTH Bleeding Criteria (15, 16)

Major bleeding
 
 • Clinically overt bleeding that is associated with: 
 o A fall in hemoglobin of 2 g/dL (24 mmol/L) or more, or o A transfusion of 2 or more units of wholeblood or packed red blood cells, or o Symptomatic bleeding in a critical site or organ such as: intracranial, intraspinal, intraocular, retroperitoneal, pericardial; intra-articular, intramuscular with compartment syndrome, or o A fatal outcome

Clinically relevant non-major (CRNM) bleeding
 
 • Any sign or symptom of hemorrhage (e.g., more bleeding than would be expected for a clinical circumstance, including bleeding found by imaging alone) that does not fit the criteria for the ISTH definition of major bleeding but does meet at least one of the following criteria: 
 o requiring medical intervention by a healthcare professional o leading to hospitalization or increased level of care o prompting a face to face (i.e., not just a telephone or electronic communication) evaluation. 
Minor
 
 • Bleeding episodes not requiring any medical attention and therefore not meeting the criteria for major or clinically relevant non-major bleeding.

Please refer to Section 7.3 for other details on endpoint definitions.

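### The plan does not say how deaths outside the endpoint are handled and names only Kaplan-Meier for cumulative rates; if those deaths are censored at death, one-year bleeding incidence is modestly overstated

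*Combined protocol and SAP*

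**What the plan says.** Section 11.4 sets one analysis for all primary and secondary endpoints: a Cox model for time to first adjudicated event, with cumulative rates described by a single named method: "cumulative event rates over time are summarized using the Kaplan-Meier method". It also promises that "appropriate summary statistics (e.g. event rate) including 95% CI will be provided", without naming the estimator behind that rate.

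Subjects without the event are "censored at the last date of the analysis period or at the last date of known outcomes status", and the second date is for subjects whose follow-up is incomplete. Section 11.2 adds two general statements: "Data on subjects who do not reach a specific endpoint will be censored in the corresponding statistical analyses", and "Follow-up is censored at the last date of known follow-up status in subjects with incomplete follow-up". None of these names death, and no section mentions competing risks or a cumulative incidence function.

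Section 7.1 defines the endpoint: "The primary endpoint is the composite of major or clinically relevant non-major bleeding (MCRB"). Fatal bleeding is inside it, because the ISTH table in section 17.3 lists "A fatal outcome" among the criteria for major bleeding. Death without a bleed is outside it. Section 7.2 also has single components analysed, and only one of its composites includes death from any cause.

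Both primary decisions (sections 11.4.1.1 and 11.4.1.2) rest on the upper 95% limit of the Cox hazard ratio, below 1.20 and then below 1.00. Neither uses a Kaplan-Meier rate.

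**The concern.** A subject who dies without a bleed can no longer have one. If that death is treated as ordinary censoring, 1-KM estimates the risk in a hypothetical population in which nobody dies of anything else. It cannot be lower than the proportion who actually bleed within the year. The same holds for stroke, MI, stent thrombosis and the bleeding categories taken singly.

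Readers weigh bleeds avoided against ischaemic events on the absolute one-year scale, so the rate per arm and its difference should describe what happens to real patients. If mortality differs by arm, the two arms are also inflated by different amounts.

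The missing rule matters a second time because the same censoring sentence governs the Cox model. A death on Day 100 could be censored on Day 100 as the last known status, or carried event-free to Day 365 as the end of the period. These choices estimate different hazard ratios.

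**Working it through.** **Inputs.** From section 11.9: one-year MCRB 24% (VKA) and 18% (edoxaban), exponential times, two-sided alpha 0.05, 80% power, 712 evaluable and 750 enrolled per arm. One-year non-bleeding mortality is not given; I assume 2% to 10%.

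**The plan's own figures.**
- Hazards: VKA −ln(0.76) = 0.2744; edoxaban −ln(0.82) = 0.1985. HR = 0.1985/0.2744 = 0.7231, as stated.
- Events: 4(1.960 + 0.842)²/(ln 0.7231)² = 298.7, so 299. Mean event probability is (0.24 + 0.18)/2 = 0.21, and 299/0.21/2 = 712 per arm, as stated.

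**Reading A: deaths censored at the date of death.** With constant bleeding hazard b and death hazard d = −ln(1 − mortality):
- 1-KM at one year = 1 − exp(−b)
- cumulative incidence = b/(b + d) × [1 − exp(−(b + d))]

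Example for VKA at 5% mortality: d = 0.0513, b + d = 0.3257, and 0.2744/0.3257 × (1 − 0.76 × 0.95) = 0.8425 × 0.278 = 23.4%.

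| Assumed mortality, both arms | VKA (KM 24.0%) | Edoxaban (KM 18.0%) | Risk difference (KM 6.0) |
|---|---|---|---|
| 2% | 23.8% | 17.8% | 5.9 |
| 5% | 23.4% | 17.6% | 5.9 |
| 8% | 23.1% | 17.3% | 5.8 |
| 10% | 22.8% | 17.1% | 5.7 |

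The overstatement is 0.2 to 1.2 points (VKA) and 0.2 to 0.9 points (edoxaban). The risk ratio stays at 0.75. A component with a 3% rate shifts by 0.03 to 0.15 points.

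Unequal mortality:
- 5% VKA, 8% edoxaban: 23.42 − 17.29 = 6.1 points.
- 8% VKA, 5% edoxaban: 23.07 − 17.56 = 5.5 points.

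Timing matters little. In simulations with bleeding, death or both front-loaded (Weibull shape 0.5), the 24% became 23.2% to 23.7% at 5% mortality and 22.7% to 23.3% at 8%.

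**Reading B: deaths carried event-free to Day 365.** The Day-365 figure is then essentially the cumulative incidence, so it is not overstated. The Cox model, however, keeps dead subjects in the risk set and in effect estimates a subdistribution hazard ratio, approximately ln(1 − incidence, edoxaban)/ln(1 − incidence, VKA):
- 5% VKA, 8% edoxaban: ln(0.8271)/ln(0.7658) = 0.1899/0.2669 = 0.71.
- 8% VKA, 5% edoxaban: ln(0.8244)/ln(0.7693) = 0.1931/0.2623 = 0.74.
- 5% in both arms: 0.1931/0.2669 = 0.724.

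The cause-specific value is 0.723 throughout.

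**Effect on power under reading A.** Competing deaths remove some bleeding events. Superiority power at 2 × 750 is 81.7%, 81.1%, 80.5% and 80.1% at 2%, 5%, 8% and 10% mortality, with no other loss to follow-up.

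**The case against.** The strongest reply is that nothing is shown to be overstated. The overstatement needs deaths to be censored at death, which the protocol does not say; under the other reading it disappears. That stands, and it is why the point is conditional.

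A reader might go the other way and infer that the text definitely keeps dead subjects at risk to Day 365. The documents do not support that either. The last date of known outcome status is set subject by subject, and a date of death fits it naturally.

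The effect is also small beside sampling error. With 750 per arm, the 95% half-width is 1.96 × √(0.24 × 0.76/750) = 3.1 points on the VKA rate and 1.96 × √((0.24 × 0.76 + 0.18 × 0.82)/750) = 4.1 points on the difference. That stands on size. But the bias always runs upward, and a larger trial would not remove it.

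Kaplan-Meier alongside a cause-specific Cox model is coherent, and 1-KM estimates a defined quantity. This justifies keeping it as a supplement, but not as the only estimate of one-year risk.

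Finally, the synopsis leaves analysis details to a SAP whose text is not in the document reviewed. The SAP may settle the matter. Section 11.4 nevertheless already fixes the estimator, and no section reviewed resolves how deaths are handled.

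**Conclusion.** The point holds as a minor improvement to descriptive rates plus one missing rule. Under date-of-death censoring, the Kaplan-Meier figures exceed the cumulative incidence by about 0.2 to 1.2 points on 24% and 0.2 to 0.9 points on 18%. The risk difference moves from 6.0 to between 5.9 and 5.7 points with equal mortality, and to 6.1 or 5.5 points at 5% against 8%. These sizes rest on an assumed 2% to 10% non-bleeding mortality and, for the main figures, on constant hazards. The only related information is that section 4.1.2 excludes subjects with a life expectancy under 12 months.

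A reader might infer that the primary analysis or sample size is flawed. The documents do not support that. With deaths censored at death, the Cox model gives a valid cause-specific hazard ratio, the decision rule does not use Kaplan-Meier, and power stays at or above 80% over the assumed range. Only if deaths were carried to Day 365 would the primary hazard ratio change its meaning, to about 0.71 or 0.74 instead of 0.723 in the unequal-mortality examples.

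Nor are all endpoints affected alike. The all-cause-death composite is untouched, fatal bleeding already counts as an event, and composites with CV death are affected only through non-CV death.

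**What to change.** In section 11.4, with matching text in the synopsis and the SAP:

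- State that a subject who dies without the endpoint is censored at the date of death in the Cox model, and that the hazard ratio is cause-specific.
- For MCRB and every endpoint that does not include all-cause death, report the Day-365 Aalen-Johansen cumulative incidence per arm, with death outside the endpoint as the competing event, and the risk difference with 95% CI.
- Keep Kaplan-Meier as a supplement if wanted, and as the main estimate for the all-cause-death composite.
- Name the estimator behind the event rate with 95% CI.

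The cost is wording and a little programming. No new data are needed: section 17.1.2 has all deaths adjudicated, and sections 6.5 and 6.5.1 provide for collecting vital status. Reported rates will be slightly lower than the Kaplan-Meier figures.

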11.4.1. Analysis of the primary endpoint

The primary endpoint is defined as the composite of major or clinically relevant non-major bleeding (MCRB) defined according to the ISTH-defined bleeding definitions (see section 7.3).

There are two primary hypotheses for the primary endpoint to be tested in this study.

- The edoxaban-based antithrombotic regimen is non-inferior to the VKA-based antithrombotic regimen with regards to MCRB.
- The edoxaban-based antithrombotic regimen is superior to the VKA-based antithrombotic regimen with regards to MCRB.

These two hypotheses are tested in a hierarchical manner, non-inferiority followed by superiority to control the type-I error rate, with adequate power for each of the two hypotheses.

11.4.1.1. Test for non-inferiority

The *primary analysis to show non-inferiority* will be based on first occurrence of an (adjudicated) MCRB that occurred during the 'overall study period' for all subjects belonging to the ITT analysis set and applying the aforementioned statistical method. The edoxaban-based regimen will be considered non-inferior to the VKA-based regimen, if the upper boundary of the two-sided 95% CI for HR falls below 1.20.

To evaluate the robustness of the primary analysis, the analysis will be repeated using the mITT and PP analysis set. In addition, the statistical results based on the following analysis periods: 'initial dose to final dose+ 30 days', 'overall study period+ 30 days' will be presented but should be interpreted in a more descriptive way. Results for other combinations of analysis sets and analysis periods may be presented if considered necessary.

11.4.1.2. Test for superiority

The *primary analysis to show superiority* will be based on first occurrence of an (adjudicated) MCRB that occurred during the 'overall study period' for all subjects belonging to the ITT analysis set and applying the aforementioned statistical method. The edoxaban-based regimen will be compared with the VKA-based regimen for superiority only if the non-inferiority of the edoxaban based regimen is established first. The edoxaban-based regimen will be considered superior to the VKA-based regimen, if the upper boundary of the two-sided 95% CI for HR falls below 1.00.

To evaluate the robustness of the primary analysis, the analysis will be repeated using the mITT and PP analysis set. In addition, the statistical results based on the following analysis periods: 'initial dose to final dose + 30 days', 'overall study period + 30 days' will be presented but should be interpreted in a more descriptive way. Results for other combinations of analysis sets and analysis periods may be presented if considered necessary.

11.4.2. Analysis of the secondary exploratory endpoints

The *main analysis for all secondary exploratory endpoints* will be based on first occurrence of an (adjudicated) endpoint during the 'overall study period' for all subjects belonging to the ITT analysis set and applying the aforementioned statistical method.

There will be no formal statistical testing for secondary exploratory endpoints. HRs, CI and p-values are provided but should be interpreted in a purely descriptive exploratory manner.

To evaluate the robustness of the main analyses, the analysis will be repeated using the mITT and PP analysis set. In addition, the statistical results based on the following analysis periods: 'initial dose to final dose + 30 days', 'overall study period + 30 days' will be presented but should be interpreted as supportive. Results for other combinations of analysis sets and analysis periods may be presented if considered necessary.

11.4.3. Pharmacokinetic/Pharmacodynamic Analysis

11.4.3.1. Pharmacokinetic Analyses

Not applicable (there will be a separate sub-study protocol) (please refer to section 17.2).

11.4.3.2. Pharmacodynamic Analyses

Not applicable.

11.4.3.3. Biomarker Analyses

Not applicable (there will be a separate sub-study protocol) (please refer to section 17.2).

11.4.3.4. Pharmacogenomic Analyses

Not applicable.

11.4.4. Health Economics Outcome Research (HEOR) Analyses

Not applicable (there will be a separate sub-study protocol) (please refer to section 17.2).

11.5. Safety Analyses

11.5.1. Adverse Event Analyses

Adverse events meeting the criteria defined in Section 9.1 will be recorded in the eCRF and coded by system organ class and preferred term using the Medical Dictionary for Regulatory Activities (MedDRA), version 19.1 or newer.

Treatment-emergent adverse events (TEAEs) are defined as events which start on or after any first dose of the assigned study medication regimen or started prior to but then worsened after any first dose of the assigned study medication regimen. An AE that occurs more than 30 days after the date of the last dose of the assigned study medication regimen will not be counted as a TEAE.

The AE analysis will be based on the SAF analysis set. TEAEs will be summarized by treatment group. The incidence of TEAEs will be presented by treatment group, by relationship to the assigned study regimen, and by severity. If more than one AE is coded to the same preferred term for the same subject, the subject will be counted only once for that preferred term using the greatest severity and strictest causality for the summarization by severity and causal relationship. Frequent TEAE (reported by at least 5% resp. 1% of subjects in any treatment group) will be summarized by regimen group.

The incidence of death, SAEs, drug-related SAEs, and AEs leading to permanent discontinuation of the assigned study regimen will be summarized. All AEs meeting the criteria defined in Section 9.1 will be included in a data listing and a listing to display the coding of AEs will be prepared as well.

11.5.2. Clinical Laboratory Evaluation Analyses

The clinical laboratory evaluations for each scheduled test, including elevated liver enzymes and/or bilirubin, and the change from baseline will be summarized for the SAF analysis set by treatment regimen. Shift tables (in categories of low, normal, and high) will be provided for each treatment regimen for selected laboratory parameters. Also, the number and percentage of subjects with clinically relevant abnormal laboratory values while on study drug will be calculated for each treatment regimen for selected laboratory parameters. All abnormal laboratory values will be presented in a listing.

Details will be outlined in the SAP.

11.5.3. Vital Sign Analyses

Vital signs at each evaluation point and the change from baseline will be summarized for the SAF analysis set by treatment regimen. The number and percentages of subjects with abnormal vital signs while on study drug will be summarized by treatment regimen.

11.5.4. Electrocardiogram Analyses

The ECG evaluations at baseline, Month 1, Month 3, Month 6, Month 9, Month 12 and at FU visit will be summarized by treatment regimen. More details on the ECG analysis will be given in the SAP.

11.5.5. Physical Examination Analyses

Physical examination will only be performed at the baseline visit.

Counts and percentages of physical examination findings will be summarized by treatment regimen based on SAF analysis set.

11.6. Other Analyses

Details on the Syntax Score and hospitalisations analyses will be given in the SAP.

11.7. Interim Analyses

Not applicable.

11.8. Data and Safety Monitoring Board (DSMB)

There will be an independent DSMB to protect the rights, safety and well-being of subjects participating in this study. The DSMB will be involved in the management of this clinical study serving as the safety monitoring advisory group for the study. The primary role of the DSMB will be to examine the safety data (incidence of MCRB or MEE, or suspected related (S)AEs) on an ongoing basis in a unblinded manner to ensure a prompt identification of any safety issues and to alert the Executive Committee in case of any clinically concerning safety issues.

The frequency and extent of the data reviews by the DSMB, details about the reviews and stopping rules or criteria for evaluating need for study protocol modifications will be described and specified in the DSMB charter.

11.9. Sample Size Determination

The sample size determination for the study was driven by requirements for testing superiority of the edoxaban-based regimen over the VKA-based regimen as described above.

The power calculation was based on a test using the Cox proportional hazards model and was performed with PASS version 14.0.4, with the module for two survival curves using Cox's proportional hazards model) under the ITT principle with a fixed follow-up time of 12 months (i.e., 365 days).

Based on a review of available safety data, the estimated one-year event rate of the primary endpoint (MCRB, i.e. ISTH major or clinically relevant non-major bleeding) under the VKA-based antithrombotic regimen is 24%-(13, 27, 28). The edoxaban-based antithrombotic regimen is anticipated to reduce the one-year incidence to 18% (a relative risk (RR) of 0.75). Under the assumption of an exponential distribution, the hazard ratio (HR) equals 0.7231.

The accrual of 2 x 712 evaluable subjects provides 80% power to demonstrate superiority of the edoxaban-based antithrombotic regimen over the VKA-based

antithrombotic regimen at a two-sided $\alpha=0.05$. To compensate for loss-to-follow-up within 12 months, the final sample size is set at 2 x 750 subjects.

With this sample size, the study has 82% power to show non-inferiority (with a margin of 1.20) if the underlying HR is 0.88 at a one-sided significance level of 2.5%.

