- Main thromboembolic event, defined as composite of cardiac or thromboembolic death (thromboembolic death considered to be thromboembolic in origin (including thromboembolic stroke, pulmonary embolism, any other

systemic embolism), ischemic stroke, SEE, spontaneous MI and definite stent thrombosis.

- ISTH-defined major bleeding
- Any bleeding defined as the composite of major, clinically relevant non-major and minor bleeding (ISTH definition)

- - -- Symptomatic-intracranial-hemorrhage.OGH) -----

Composite of stroke and SEE

Composite of all-cause death, stroke, SEE, spontaneous MI and definite stent thrombosis

Composite of CV death, spontaneous MI and definite stent thrombosis

- The single components of the composite primary and secondary endpoints mentioned above are explored, as well as specific subcategories (e.g., hemorrhagic, ischemic and undetermined stroke)

Safety parameters such as (serious) adverse events, laboratory parameters, ECG and vital signs.

All secondary endpoints are analyzed as time to first occurrence of any of its components.

Bleeding events are also classified according to Bleeding Academic Research Consortium (BARC) and Thrombolysis in Myocardial Infarction (TIMI) classifications for descriptive purposes only. All suspected bleeding events are adjudicated by the CEC in a blinded manner.

All events are also sub-categorized into fatal and non-fatal.

For all endpoints blindly adjudicated by the CEC, the CEC's interpretation prevails and is used in the statistical analyses.

Planned Sample Size: The plan is to enroll 1500 subjects (750 per arm).

Based on a review of available safety data, the estimated one-year event rate of the primary endpoint (MCRB, i.e. ISTH major or clinically relevant non-major bleeding) under the VKA-based antithrombotic regimen is 24%. The edoxaban-based antithrombotic regimen is anticipated to reduce the one-year incidence to 18% (a relative risk (RR) of 0.75). Under the assumption of an exponential distribution, the hazard ratio equals 0.7231. The accrual of 2 x 712 evaluable subjects provides 80% power to demonstrate superiority of the edoxaban-based antithrombotic regimen over the VKA-based antithrombotic

regimen at a two-sided $\alpha=0.05$. To compensate for censoring, the final sample size is set at 2 x 750 subjects.

Statistical Analyses: Four analysis sets are defined:

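### Section 11.9 gives superiority power on 2 x 712 evaluable subjects but non-inferiority power on all 2 x 750 enrolled; on a common basis the stated 82% is about 80-81%

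*Combined protocol and SAP*

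**What the plan says.** Protocol section 11.9 builds the sample size in three steps.

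- **Superiority.** The VKA one-year rate of major or clinically relevant non-major bleeding is taken as 24% and the edoxaban rate as 18%. "Under the assumption of an exponential distribution, the hazard ratio (HR) equals 0.7231". The power claim that rests on these figures reads: "The accrual of 2 x 712 evaluable subjects provides 80% power to demonstrate superiority".
- **Allowance.** "To compensate for loss-to-follow-up within 12 months, the final sample size is set at 2 x 750 subjects". The synopsis (Planned Sample Size) gives a different reason for the same increase: "To compensate for censoring, the final sample size is set at 2 x 750 subjects". Neither place states an attrition rate.
- **Non-inferiority.** "With this sample size, the study has 82% power to show non-inferiority (with a margin of 1.20) if the underlying HR is 0.88". The test is one-sided at 2.5%. The natural antecedent of the sample size meant here is the 2 x 750 named just before. No event rate and no allowance for loss are given for this scenario.

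The non-inferiority criterion in section 11.4.1.1 is met "if the upper boundary of the two-sided 95% CI for HR falls below 1.20", which matches a one-sided 2.5% test. Sections 11.2 and 11.4 censor subjects with incomplete follow-up at their last known status.

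**The concern.** The 38 extra subjects per arm are enrolled because some follow-up is expected to be lost. The superiority power leaves them out; the non-inferiority power appears to count them as fully observed. A reader who sets 80% beside 82% would conclude that non-inferiority at a hazard ratio of 0.88 is slightly better powered than superiority at 0.7231. If the difference comes only from the denominator, that comparison is an artefact, and 82% is a no-loss figure placed directly after a sentence that expects loss. What is at stake is the accuracy of a power statement that may be repeated in the study report, not the design.

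**Working it through.** **Inputs from section 11.9:** VKA one-year rate 24%; edoxaban 18% for superiority; exponential survival; fixed 12-month follow-up; 712 evaluable and 750 enrolled per arm; margin 1.20; true hazard ratio 0.88; one-sided 2.5% (z = 1.96). Allocation is 1:1 (section 5.1).

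**Assumptions:** the 24% VKA rate also applies to the non-inferiority case; the loss is 38/750 = 5.07% per arm, back-calculated from 712 and 750.

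**Step 1. Reproduce the superiority figure.**
- HR = ln(0.82)/ln(0.76) = 0.7231, as stated.
- Events D = 712 x (0.24 + 0.18) = 299.0.
- Power = Φ(√(D/4) x |ln 0.7231| − 1.96) = Φ(8.646 x 0.3242 − 1.96) = Φ(0.843) = 80.0%, as stated.

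The events formula for a Cox test therefore matches the plan's own method.

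**Step 2. Apply it to non-inferiority.**
- Edoxaban rate at HR 0.88: 1 − 0.76^0.88 = 21.46%.
- Power = Φ(√(D/4) x ln(1.20/0.88) − 1.96), with ln(1.20/0.88) = 0.3102.
- 2 x 750, no loss: D = 750 x (0.24 + 0.2146) = 340.9; Φ(9.232 x 0.3102 − 1.96) = Φ(0.903) = 81.7%. This rounds to the stated 82%.
- 2 x 712: D = 712 x 0.4546 = 323.6; Φ(8.995 x 0.3102 − 1.96) = Φ(0.830) = 79.7%.

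**Step 3. Let lost subjects keep partial follow-up.** If 38 per arm leave uniformly over the year, the chance of an event before leaving is 12.55% on VKA and 11.16% on edoxaban.
- D = 323.6 + 38 x (0.1255 + 0.1116) = 323.6 + 9.0 = 332.7 (unrounded 332.65).
- Power = Φ(9.119 x 0.3102 − 1.96) = Φ(0.868) = 80.7%.
- Exponential instead of uniform loss times give 332.6 events and the same 80.7%.

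**Step 4. Compare on a common basis.**

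| Basis | Superiority, HR 0.7231 | Non-inferiority, HR 0.88 |
|---|---|---|
| 2 x 712 evaluable | 80.0% | 79.7% |
| 2 x 750, 5.07% censored during the year | 81.1% | 80.7% |
| 2 x 750, complete follow-up | 82.0% | 81.7% |
| As stated in section 11.9 | 80% | 82% |

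The stated pair takes its first figure from the top row and its second from the third.

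**Step 5. Sensitivity to the formula** (2 x 750 without loss, then 2 x 712): edoxaban rate taken as 0.88 x 24%, 81.4% and 79.4%; variance 1/d1 + 1/d2, 81.6% and 79.5%; Freedman-type, 81.1% and 79.0%. The gap of about 2 points does not depend on the approximation.

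**The case against.** The strongest reply is that nothing is miscalculated. The sentence refers to the final sample size, that size is 2 x 750, and at 2 x 750 the power is 81.7%. This stands: a reader might infer an arithmetic error, and the documents do not support that. What is missing is the allowance for loss, or a statement that none was made.

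Second, the cause is inferred. Other event rates would also give 82% after loss. With the hazard ratio held at 0.88, a VKA rate of about 25.2% at 2 x 712 gives 81.6%, and about 24.5% at 2 x 750 with 38 per arm lost uniformly gives 81.5%. An event rate of 24% in both arms at 2 x 712 gives 341.8 events and 81.8%, but that conflicts with a true hazard ratio of 0.88. The caveat stands: the result is conditional on the 24% rate, the only VKA rate section 11.9 gives.

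Third, dropping the 38 per arm entirely is harsher than the planned analysis. The synopsis speaks of censoring, sections 11.2 and 11.4 censor at last known status, and section 6.5 continues data collection when visits stop. This stands too, and favours 80.7% over 79.7%.

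Fourth, a reader might infer that the lower figure endangers superiority, because non-inferiority is tested first. It does not. Both tests use the same ITT set, period, Cox model and 95% interval, and an upper limit below 1.00 is always below 1.20, so the first step cannot block the second. At the design hazard ratio of 0.7231 with 299.0 events, non-inferiority power is Φ(8.646 x ln(1.20/0.7231) − 1.96) = Φ(2.42), about 99%. Nor is the claim of adequate power for both hypotheses contradicted: the documents set no numerical threshold, and power stays near 80% on every basis.

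**Conclusion.** The point holds as a minor correction. Section 11.9 reports two powers on different bases. With the 24% VKA rate carried over and the loss of 5.07% per arm implied by 712 and 750, non-inferiority power at a hazard ratio of 0.88 is about 80-81%: 80.7% under censoring as the analysis specifies, 79.7% if lost subjects contribute nothing. The stated 82% requires complete follow-up of all 1500. The overstatement is 1 to 2 points. Both the event rate for this scenario and the loss rate are inferred, because the plan states neither. The finding does not show a faulty formula, an underpowered trial or a threat to the superiority test.

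**What to change.** Replace the last sentence of section 11.9 with one that names its basis, for example:

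*Allowing for the anticipated loss to follow-up (2 x 712 evaluable of 2 x 750 enrolled) and assuming a 24% one-year rate under VKA, power for non-inferiority (margin 1.20, one-sided 2.5%) is approximately 80-81% at a true hazard ratio of 0.88; 82% applies only with complete follow-up of all 1500 subjects.*

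If the sponsor used another event rate, state it and give the power after loss at that rate. It would also help to give the assumed loss rate and to use one term for the allowance in the synopsis and section 11.9.

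The cost is one sentence and a stated power 1 to 2 points lower. Enrolment, margin, analysis and decision rule do not change.
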